4.1 Inclusion criteria

Adult (18 years and older) ED patients with all of the following (all determined pre-randomization):

1. VESTIBULAR SYMPTOMS: presenting symptom of “vertigo” OR “dizziness” OR “unsteadiness” (as defined by consensus expert definitions in the International Classification of Vestibular Disorders²⁵)
2. RELEVANT EXAM SIGNS*: pathologic nystagmus (spontaneous, gaze-evoked, or positional) by bedside VOG testing OR pathologic ataxia (gait, trunk, stance, limbs) by bedside ataxia examination
3. RECENT ONSET: symptoms AND signs* appear to be new or markedly worse in the past month

* Exam signs are required for randomization, but not for the observational arm

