Procedurally, the patient will be randomized electronically, with their VRT algorithm diagnosis determined electronically. If the patient is randomized to the VRT (intervention) arm, the on-call expert reviewer at the Coordinating Center will be notified (regardless of site) and the entire VOG recording will be available for immediate review and playback, in real time, along with key historical data. The review process is expected to take ~10-15 minutes. The review includes viewing a room camera of the test procedures, eye camera of the eye movements, and quantitative traces of eye and head. If necessary, the reviewer may contact the study coordinator to seek additional information. The double-check expert review procedure will NOT apply to those in the standard care arm (only those in the VRT arm).

In the VRT arm, the selected diagnosis is linked to the prespecified management recommendation per diagnosis. If the ED provider has any concerns with VRT-diagnostic category or specified management, they will be given the opportunity to talk with the reviewing vestibular specialist, if applicable, and if so desired. For as long as this human double-check procedure remains in place, any VRT-arm care recommended by the expert reviewer and endorsed by the ED physician will be considered clinically-indicated for billing purposes. For example, if the VRT algorithm suggests the patient has a vestibular neuritis, but the human reviewer changes the category to stroke, then the prespecified management pathways (including the stroke-related care) is considered clinically-indicated (e.g., ED index visit MRI, hospital admission). Alternatively, if the VRT algorithm returns an “equivocal” result and the expert reviewer changes the category to a specific vestibular condition, then the prespecified pathway for the vestibular condition (e.g., requires vestibular function testing for Menière’s disease) will also be considered clinically-indicated.

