The rationale for obtaining the delayed gold-standard MRI is that the sensitivity of MRI for detecting stroke is much greater at days 3-7 than in the first 72 hours after onset of symptoms. MRI sensitivity (using diffusion-weighted imaging [DWI] optimized for stroke detection) rises sharply in the first few hours after the onset of stroke symptoms. False negative scans are more frequent in the first 24 hours after onset of posterior fossa stroke symptoms than in the subsequent period from 24-72 hours after onset. MRI sensitivity is about 80%²⁹ <24 hours and about 86%⁷³ <72 hours. Maximal MRI sensitivity (~99%⁷³) is achieved after about 72 hours, and is maintained at a high level until ~14 days after onset of symptoms, then declines to a nadir around 1 month.¹⁰⁷ Accordingly, only those whose gold-standard MRI scans were obtained within the 14-day period will be included as part of the primary analysis for the main trial outcome (see Statistical Analysis Plan below).

Oral anxiolytic therapy may be offered to subjects per local institutional policy who have MRI anxiety. This will be documented in the subject's record and same-day follow-up assessments that may be affected by anxiolysis (e.g., vestibular testing) must be completed prior to anxiolytic administration.

MRIs will be read by two independent, masked study neuro-radiologists. For safety, all 1-week study MRIs will also be read clinically as an urgent ED scan by on-site clinical radiologists.

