Analytic approach: For all primary and linked secondary analyses, we will include only randomized subjects completing the essential elements of the diagnostic study protocol through the end of 1-week follow-up (i.e., with ED index visit VOG test results, follow-up MRI within 14 days, and an in-person neuro-otology visit within 30 days of the index visit). The quality of VOG and MRI testing will be determined by masked, expert raters from the FDAC during an FDAC meeting pre-review process; if either essential test is deemed to be of insufficient quality for analysis (e.g., key VOG tests performed improperly or missing; motion artifact on MRI), such patients will be excluded from the primary and linked secondary analyses of the main trial outcomes. This per-protocol analysis is appropriate for this Phase II study designed to determine the potential efficacy of the VRT intervention on diagnostic accuracy. Without adequate quality VOG and 1-week follow-up data, diagnoses will remain speculative. Subjects lost to follow-up at the 30-day time point (phone follow-up) will be included in these analyses, as 1-month medical record review will generally be sufficient to determine correct diagnoses.

Definitions: For the purposes of all analyses, the term “stroke” refers to any acute cerebrovascular event (ischemic stroke, transient ischemic attack, intracranial hemorrhage), unless expressly specified otherwise.

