2. STATISTICAL ANALYSIS PLAN

2.1 General Design Issues

Main trial design: Randomized controlled trial (individual patient randomization), parallel design (1:1). Results will be used for primary outcome analyses related to diagnosis accuracy at the ED index visit.

Secondary cohort design: Cohorts will be followed for adverse events and functional outcomes (1wk, 30d). Estimates will be used for phase 3 trial planning for the impact of diagnosis accuracy on clinical events and outcomes. The 6-month follow-up time point (if available) will not be part of the primary trial outcomes.

Observational arm: Patients with vestibular symptoms but no signs or who are not randomized for other reasons (see Inclusion and Exclusion Criteria) will be eligible for a parallel track observational sub-study with limited phone follow-up.

Diagnosis adjudication: Prior to adjudication, index VOG results will be interpreted by two independent vestibular experts masked to allocation. They will be given only patient demographic information, a structured summary of dizziness-related history of the present illness, and bedside hearing test results. Using this information, and masked to all other index visit clinical findings, ED physician diagnoses, any neuroimaging, and all follow-up data, they will render an ED index visit diagnosis (“Index VOG Diagnosis”). Prior to adjudication, MRIs will be interpreted by two independent neuro-radiologists masked to allocation and all clinical findings other than demographic information. They will render an index visit diagnosis (“Index Radiology Diagnosis”). A 5-member multidisciplinary panel with ED physician, otolaryngologist, vestibular neurologist, stroke neurologist, and neuro-radiologist will adjudicate diagnoses. The panel will be masked at all times to trial allocation (VRT vs. standard care). Diagnoses will be classified into 1 of 6 diagnostic categories likely to affect ideal ED management and rated as probable or definite based on neuroimaging results and standard clinical criteria. Diagnoses will be rendered in two stages – first based on VOG and all clinical data (including eye videos) from the ED index visit alone, without follow-up data (“Adjudicated Index Diagnosis”); then again after all 1-week testing and 30-day follow-up data are revealed electronically (“Adjudicated Final Diagnosis”). All differences will be resolved by discussion or majority vote.

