where $Y_i(0)$ is the variable indicating correct or incorrect diagnoses in SOC arm as defined in Aim 1, $\overline{Z_i}$ are additional subgroups variables or other covariates listed in Aim 1.

In addition, standard time-to-event analyses (Kaplan-Meier,¹⁶³ Cox regression¹⁶⁴) will be used to estimate relative hazard ratios, adjusting for demographic and clinical variables listed in Aim 1.

Exploratory Outcomes:

1. Preventable Six-Category Diagnosis Error (all, VRT vs. SOC)

Total diagnosis inaccuracy (error) VRT vs. SOC using adjudicated index diagnoses categorized in one of six diagnosis categories (3 peripheral, 1 central, 1 medical/other, 1 non-diagnosis). Adjudicated index diagnoses will be determined using only ED index visit data that “would have been” available clinically (i.e., excluding safety MRI, index hospital admission data, and all follow-up data).

2. VRT vs. MRI Stroke-No Stroke Diagnosis Accuracy (VRT arm only, VRT vs. MRI)

Total diagnosis accuracy VRT vs. index imaging using 30-day adjudicated final diagnoses categorized as stroke vs. no stroke (posterior fossa mass lesion, encephalitis, etc.). The VRT arm is chosen here because all VRT arm patients will undergo MRI at the index visit (protocol, clinical, or safety), eliminating diagnostic ascertainment bias that may be present in the SOC arm.

3. Algorithm-Only VRT Six-Category Diagnosis Accuracy (all, initial VRT output vs. SOC)

Total diagnosis accuracy “as computed in real time,” algorithm-only VRT diagnosis vs. SOC using 30-day adjudicated final diagnoses categorized in one of six diagnosis categories (3 peripheral, 1 central, 1 medical/other, 1 non-diagnosis). We will use “Index VRT Diagnosis” and “ED SOC

Diagnosis" compared to the "Adjudicated Final Diagnosis" based on ED index visit and 30-day follow-up clinical assessments. This outcome measure reflects the weighted average diagnostic accuracy of the various versions of the automated algorithm as it would have been absent human double-check during the course of the trial.

4. Optimized Six-Category Within-Subject Accuracy (SOC arm only, optimized VRT vs. SOC)

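### Counting TIA as stroke in the VRT-versus-MRI comparison can only penalise MRI on TIAs without a lesion, and may favour VRT by an amount the plan does not bound

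*SAP*

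**What the plan says.** The comparison appears in SAP 2.2 as exploratory outcome 2 and in Protocol 9.2.1 as secondary outcome 4: "Total diagnosis accuracy VRT vs. index imaging using 30-day adjudicated final diagnoses categorized as stroke vs. no stroke". It uses the VRT arm only, because every patient there is to have an index MRI.

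The meaning of stroke is set once, in Protocol 9.1, for all analyses: the term "refers to any acute cerebrovascular event (ischemic stroke, transient ischemic attack, intracranial hemorrhage), unless expressly specified otherwise". The SAP does not repeat this definition. Neither version of the outcome overrides it, and the examples of 'no stroke' that they give (mass lesion, encephalitis) do not include TIA.

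Three parties work from different information:

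- **MRI reading.** SAP 2.1: "MRIs will be interpreted by two independent neuro-radiologists masked to allocation and all clinical findings other than demographic information". The outcome does not name the reading it uses; this is the only imaging diagnosis that SAP 2.1 defines.
- **VRT diagnosis.** It rests on the eye-movement tests. While the human double-check is in force, Protocol 5.1.3 adds that "the entire VOG recording will be available for immediate review and playback, in real time, along with key historical data".
- **Reference panel.** It works in two stages, "first based on VOG and all clinical data (including eye videos) from the ED index visit alone, without follow-up data", and then with the 1-week and 30-day data added. The outcome uses the second-stage diagnosis.

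**The concern.** MRI can be credited with a stroke only if the images show one. Where a patient is adjudicated as TIA and the scan shows nothing acute, a faultless reading of 'no stroke' is scored as an error. VRT works from eye movements and history, so it can be scored right on the same patient. The comparison is within patient, and each such patient is a discordant pair in VRT's favour.

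This matters for interpretation. The protocol's abstract says that the eye-movement approach is more accurate than MRI in the first two days of acute continuous vertigo, and a reader will take this outcome as the trial's evidence on that claim. Protocol 6.3.18 describes early MRI's weakness as missed lesions that a later scan would show. A TIA that never shows a lesion says nothing about that weakness, yet here it is counted with those misses. No analysis without TIA is planned.

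**Working it through.** **The plan's own figures.** For 90% vs 75%, two-sided alpha 0.05 and 80% power:

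n = [1.96·√(2·0.825·0.175) + 0.8416·√(0.90·0.10 + 0.75·0.25)]² / 0.15² = 99.5, so 100 per arm.

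With continuity correction: (99.5/4)·[1 + √(1 + 4/(99.5·0.15))]² = 112.5, so 113 per arm, as stated. Expected strokes are 10-20% of 113 = 11.3 to 22.6, matching the stated 11-23 per arm. The VRT-versus-MRI comparison has no sample size of its own.

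**Inputs from the documents.**
- N = 113 in the VRT arm. The number analysed may be smaller, because Protocol 9.1 drops patients without adequate VOG or follow-up MRI.
- S = 11 to 23 strokes, not split by TIA; 17 is the midpoint.
- Early MRI sensitivity, Protocol 6.3.18: "MRI sensitivity is about 80%²⁹ <24 hours and about 86%⁷³ <72 hours".

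**Assumptions, because the documents are silent.**
- t = TIA share of reference strokes, 10-30%.
- q = share of TIAs that are lesion-negative (nothing on the images to support a stroke reading), 70-100%.
- v = share of lesion-negative TIAs that VRT calls stroke, 0-90%.

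**Formulas.**
- Lesion-negative TIAs = S·t·q.
- MRI accuracy loss, against scoring those scans as correct = S·t·q / 113.
- Contribution to the VRT-minus-MRI gap = S·t·q·v / 113.

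| S | t | q | Lesion-negative TIAs | MRI loss (points) | Gap at v = 0 / 0.5 / 0.9 (points) |
|---|---|---|---|---|---|
| 11 | 10% | 70% | 0.77 | 0.7 | 0 / 0.3 / 0.6 |
| 17 | 20% | 70% | 2.38 | 2.1 | 0 / 1.1 / 1.9 |
| 17 | 20% | 100% | 3.4 | 3.0 | 0 / 1.5 / 2.7 |
| 23 | 30% | 100% | 6.9 | 6.1 | 0 / 3.1 / 5.5 |

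**Apparent MRI sensitivity.** With 80% for all lesion-positive cases it is 0.80·(1 − t·q): 0.80·0.93 = 0.74 at the mild end and 0.80·0.70 = 0.56 at the severe end.

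**TIA counted against TIA left out.** Take S = 17 and MRI specificity 1, so that all 96 non-strokes are right.
- t = 10%, q = 70%: (0.8·17·0.93 + 96)/113 = 0.961 with TIA as stroke; (0.8·15.3 + 96)/111.3 = 0.973 without TIA patients.
- t = 30%, q = 100%: (0.8·17·0.70 + 96)/113 = 0.934 with; (0.8·11.9 + 96)/107.9 = 0.978 without.

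**When would TIA make up most of MRI's errors?** Let u = t·q. The condition is u > 0.20·(1 − u), so u > 1/6. With S = 17 and u = 10%, there are 1.7 TIA errors against 0.2·15.3 = 3.1 others. With u = 20%, there are 3.4 against 0.2·13.6 = 2.7.

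**Direction.** The gap term is zero when v = 0 and positive otherwise. Each lesion-negative TIA that VRT calls stroke adds 1/113 = 0.88 points to VRT's margin; none can add to MRI's.

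**The case against.** Several objections have force.

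- **Few TIAs may qualify.** Protocol 4.1 says: "Exam signs are required for randomization, but not for the observational arm". A patient whose signs have fully resolved is not randomized. This probably keeps t low. It does not make it zero, since signs need only be present at testing, and episodic syndromes are among the planned covariate levels.
- **VRT may miss them too.** Both methods are then wrong and the gap does not move.
- **The outcome is minor.** It is exploratory in the SAP and outside the phase 3 decision rule, and the plan concedes that the strokes are too few for firm conclusions about VOG's stroke accuracy. That limits the severity; it does not remove the one-sided scoring.
- **The broad target is legitimate.** Whether index imaging can exclude any acute cerebrovascular event is a fair ED question, and Protocol 7.V counts lost prevention after TIA among the harms of missed diagnosis. This stands, and it is why the planned outcome should be supplemented and not replaced.

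A reader might go further and infer that the panel would call such patients TIA mainly because of the VOG recording. The documents do not show that: the final diagnosis also draws on the 1-week tests and 30-day follow-up. VOG in the reference standard is a separate issue that also touches infarct cases.

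**Conclusion.** The concern holds in a limited form. Under the protocol's definition TIA is a reference-positive case in this comparison, and on a lesion-negative TIA the scoring can count only against MRI. Under the assumptions shown, MRI's total accuracy falls by about 0.7 to 6.1 points, and these cases contribute 0 to about 5.5 points to the VRT-minus-MRI gap. The signs-at-entry rule makes the lower end more likely. The documents supply none of t, q or v, so the plan does not bound the effect.

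Two stronger readings are tempting and not supported. The first is that MRI would be marked wrong largely by definition. With 80% sensitivity for the other strokes and perfect specificity, that needs lesion-negative TIAs to exceed about one in six reference strokes, a share that the documents do not give; nor do they say how often a TIA leaves no lesion. The second is that the result is tilted toward VRT as a matter of fact. It is tilted only so far as VRT calls these patients stroke, which is plausible but not shown.

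A correction is worth making because the bias runs in one direction and the data to remove it are already collected.

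**What to change.** In SAP exploratory outcome 2:

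1. State that TIA counts as stroke here under the Protocol 9.1 definition.
2. Add a prespecified companion analysis in which the reference-positive state is an adjudicated final diagnosis of ischemic stroke or intracranial hemorrhage, with patients adjudicated as TIA left out.
3. Tabulate the VRT and index MRI results of the TIA patients separately, with their number.
4. State that VRT will not be described as more accurate than early MRI for stroke unless the analysis without TIA agrees.

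Keep the broad definition for VRT versus SOC, where both sides can name a TIA. Protocol 9.1 already allows an outcome to specify its own meaning of stroke, and no new data are needed.

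The cost is a few SAP sentences, one extra analysis and one small table. The companion analysis removes a few patients by a label assigned after randomization, and it ties the reference more closely to the 1-week MRI, the same modality as one comparator; this is a further reason to report both versions. The VRT-over-MRI margin may shrink.

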Trial Arm 1 VRT (intervention arm): VOG-based logic rules determine rapid triage pathway

- report includes direct device output (physiologic traces, quantitative measures) plus most likely diagnosis, category, and clinical trial care pathway (peripheral, equivocal, central) instructions
- the VOG results become part of the patient's clinical record

The roles of the ED provider in the care of patients in the VOG arm will be as follows:

- assess illness severity and appropriateness of the patient for VOG testing and the study protocol
- exclude obvious general medical conditions
- take over diagnostic decision-making for patients in whom VOG is equivocal (with consultant input, if available)
- intervene to deviate from VRT pathway if they are concerned about safety for patients in the VOG arm

Note: these are the same roles anticipated for ED providers if the VOG device were used for clinical practice

Trial Arm 2 Standard Care (control arm): usual ED care plus VOG exam, no VOG report generated

- no VOG automated interpretation or summary report will be generated; the computer-based randomization algorithm does not generate a VOG report or pathway using logic rules in the control (standard care) arm

The roles of the ED provider in the care of patients in the standard care arm will be as follows:

- assess illness severity and appropriateness of the patient for VOG testing and the study protocol
- exclude obvious general medical conditions
- all diagnosis, consultation, treatment, and disposition decisions will be made by the treating ED provider(s)

5.1.3 Expert Human VRT Double-Check: The VRT algorithm outputs in the intervention arm will be double-checked by expert neuro-otology fellows or faculty in real time to ensure accuracy; human judgment will “trump” VRT if there is disagreement (or if, for technical reasons, the real-time algorithm is not able to be generated – for example, as with internet connectivity problems or during development). The expert human double-check procedure will be in place at the start of the main trial, and we anticipate it will remain in place until the VRT algorithm is refined (as per pre-specified adaptations during the trial period) such that it appears accurate and safe.

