Diagnostic Process: The VRT algorithm will be tuned to err on the side of caution. For example, those with prior inner ear or eye movement disorders risk confounding the results in a way that could potentially harm patients (e.g., patient with prior acoustic neuroma surgery who comes with acute, continuous dizziness due to stroke; in this patient, the exam findings related to prior surgery could lead to an erroneous “benign peripheral” diagnosis). In such cases, the algorithm will incorporate that past history and will be tuned to return an equivocal result, necessitating a neurological consultation, if available. In addition, there will be an expert human double-check for the algorithm output in the VRT arm until it is sufficiently refined (Section 5.1.3)

Identification of Adverse Effects

Safety Assessments: All safety-related assessments will be consistent with generally accepted medical practices and standard-of-care. The following specific assessments will be performed according to the schedule described in the protocol, when it is developed and approved by the DSMB. Adverse events (AEs) recorded in the source documents will be entered into the e-CRF post randomization through the index discharge. Hospitalizations and adverse events reported during the 30-day telephone interview will be recorded, including date and time of resolution, outcome, severity, relatedness and whether or not classified as a serious adverse event.

An adverse event is any untoward medical occurrence in a patient enrolled into the study whether or not it has a causal relationship to the study events. An adverse event can be any unfavorable and unintended sign (including an abnormal lab finding), symptom, or disease temporally associated to the study timeline. The investigators will follow study-related vestibular and stroke adverse events to resolution whenever possible.

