Total diagnosis accuracy “as computed in real time,” algorithm-only VRT diagnosis vs. SOC using 30-day adjudicated final diagnoses categorized in one of six possible diagnosis categories (3 peripheral, 1 central, 1 medical/other, 1 non-diagnosis). We will use “Index VRT Diagnosis” and “ED Physician Diagnosis” compared to the “Adjudicated Final Diagnosis” based on ED index visit and 30-day follow-up clinical assessments. This

outcome measure reflects the weighted average diagnostic accuracy of the various versions of the automated algorithm as it would have been absent human double-check during the course of the trial.

6. *Optimized Six-Category Within-Subject Accuracy* (SOC arm only, optimized VRT vs. SOC)

Total diagnosis accuracy optimized VRT vs. SOC using 30-day adjudicated final diagnoses categorized in one of six possible diagnosis categories (3 peripheral, 1 central, 1 medical/other, 1 non-diagnosis). We will use “Optimized VRT Diagnosis” and “ED Provider Diagnosis” compared to the “Adjudicated Final Diagnosis” based on ED index visit and 30-day follow-up clinical assessments. Optimized VRT diagnoses will be run using the final (end-of-trial) version of the VRT algorithm. Only SOC-arm subjects are used for this outcome, as VRT patient results will have been used to optimize the algorithm during the trial. VRT diagnoses in the SOC arm (algorithm not run during the trial), will be assigned based on the final, optimized algorithm; for this purpose, the ED SOC diagnosis will be assigned as the VRT diagnosis for algorithm results in the VRT-E group. This outcome measure reflects the estimated diagnostic accuracy of the end-of-trial automated algorithm.

7. *Expert VOG Six-Category Diagnosis Accuracy* (all, expert VOG vs. SOC)

Total diagnosis accuracy adjudicated expert VOG diagnosis vs. SOC using 30-day adjudicated final diagnoses categorized in one of six possible diagnosis categories (3 peripheral, 1 central, 1 medical/other, 1 non-diagnosis). We will use “Index VOG Diagnosis” and “ED Physician Diagnosis” compared to the “Adjudicated Final Diagnosis” based on ED index visit and 30-day follow-up clinical assessments. This outcome measure reflects the theoretical maximum diagnostic accuracy performance (i.e., expert level) of any future algorithms.

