Total diagnosis accuracy optimized VRT vs. SOC using 30-day adjudicated final diagnoses categorized in one of six diagnosis categories (3 peripheral, 1 central, 1 medical/other, 1 non-diagnosis). We will use "Optimized VRT Diagnosis" and "ED SOC Diagnosis" compared to the "Adjudicated Final Diagnosis" based on ED index visit and 30-day follow-up clinical assessments. Optimized VRT diagnoses will be run using the final (end-of-trial) version of the VRT algorithm. Only SOC-arm subjects are used for this outcome, as VRT patient results will have been used to optimize the algorithm during the trial. VRT diagnoses in the SOC arm (algorithm not run during the trial), will be assigned based on the final, optimized algorithm; for this purpose, the ED SOC diagnosis will be assigned as the VRT diagnosis for algorithm results in the VRT-E group. This outcome measure reflects the estimated diagnostic accuracy of the end-of-trial automated algorithm.

5. Central-Peripheral Diagnosis Accuracy (all, VRT vs. SOC)

Total diagnosis accuracy VRT vs. SOC using 30-day adjudicated final diagnoses categorized as central (stroke, posterior fossa mass lesion, encephalitis, demyelinating disease, etc.) vs. non-central (includes peripheral vestibular, medical, psychiatric, non-diagnoses, etc.).

6. Central Discharge Proportion (central subgroup only, VRT vs. SOC)

Total discharge proportion of central causes VRT vs. SOC. Central causes determined based on 30-day adjudicated final diagnosis.

7. Peripheral Admission Proportion (peripheral subgroup only, VRT vs. SOC)

Total admission proportion of peripheral causes VRT vs. SOC. Peripheral causes determined based on 30-day adjudicated final diagnosis.

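### SAP exploratory outcome 4 measures the algorithm with ED fallback, not the algorithm alone, because every equivocal result takes the ED's own diagnosis

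*SAP*

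**What the plan says.** SAP section 2.2.3, exploratory outcome 4, applies the end-of-trial algorithm to patients in whom it was not run during the trial: "Only SOC-arm subjects are used for this outcome". The comparison is within subject: "We will use 'Optimized VRT Diagnosis' and 'ED SOC Diagnosis' compared to the 'Adjudicated Final Diagnosis". When the algorithm returns an equivocal result, "for this purpose, the ED SOC diagnosis will be assigned as the VRT diagnosis for algorithm results in the VRT-E group". The outcome is then interpreted as follows: "This outcome measure reflects the estimated diagnostic accuracy of the end-of-trial automated algorithm".

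Protocol section 9.2.1, secondary outcome 6, carries the same rule ("the ED SOC diagnosis will be assigned as the VRT diagnosis for algorithm results in the VRT-E group") and the same interpretation.

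Three other places bear on the point:

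- SAP exploratory outcome 3 (algorithm-only accuracy) is interpreted in similar terms, "This outcome measure reflects the weighted average diagnostic accuracy of the various versions of the automated algorithm", but states no rule for VRT-E results.
- Protocol section 7, under Diagnostic Process, gives an example in which the algorithm should abstain. For patients with earlier inner ear or eye movement disorders, "the algorithm will incorporate that past history and will be tuned to return an equivocal result".
- Both documents list a VRT Definite-Only group that leaves out VRT-E cases. It is a potential subgroup under tertiary analysis 1 of the primary outcome and is not attached to exploratory outcome 4.

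**The concern.** The outcome has six diagnostic categories, and equivocal is not one of them, so some rule for VRT-E is needed. The chosen rule takes the missing answer from the comparator. In every VRT-E patient the two diagnoses being compared are one and the same, and they are right or wrong together. The resulting figure mixes the algorithm's performance with the ED's, in proportions set by an equivocal rate that the plan does not ask to be reported.

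What is at stake is how the figure will be read. Protocol section 9.1 restricts algorithm refinement to VRT-arm and observational data so that the SOC arm stays clean for testing the optimized algorithm. Exploratory outcome 4 is the listed analysis that uses that held-out arm for the final algorithm. A reader who takes the interpretation sentence at face value will attribute to the algorithm diagnoses that the ED provider made.

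**Working it through.** **Planning figure.** The documents state no expected value for exploratory outcome 4. The relevant figure is the SOC-arm size of 113 (SAP section 2.3, Table 3: 90% vs 75%, alpha 0.05, power 80%). The uncorrected two-sided formula gives n = [1.960·√(2·0.825·0.175) + 0.842·√(0.90·0.10 + 0.75·0.25)]² / 0.15² ≈ 99.5, or 100. The continuity correction, (n/4)·[1 + √(1 + 4/(0.15·n))]², raises this to 112.5, or 113. The stated figure is reproduced and is not in dispute.

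**Definitions.** Let e be the share of SOC-arm patients with a VRT-E result, A_D the algorithm's accuracy among committed (non-equivocal) outputs, and P_D and P_E the ED's accuracy in committed and equivocal patients.

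- Reported figure under the planned fill: (1 − e)·A_D + e·P_E
- ED accuracy in the same patients: (1 − e)·P_D + e·P_E
- Difference: (1 − e)·(A_D − P_D)
- Share of all patients diagnosed correctly by the algorithm itself: (1 − e)·A_D

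The reported figure equals A_D only if e = 0 or if P_E happens to equal A_D. At e = 100% it is exactly the ED's accuracy, and the difference is zero.

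**Numbers.** The documents do not give e, so it is varied. A_D = 95% and an ED accuracy of 75% are a row of Table 3. Setting P_D = P_E = 75% is an assumption.

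| e | Reported (filled) | Committed only | Correct by the algorithm, of all patients | Filled minus ED (points) | VRT-E not correct, minus ED (points) |
|---|---|---|---|---|---|
| 10% | 93% | 95% | 85.5% | +18 | +10.5 |
| 20% | 91% | 95% | 76% | +16 | +1 |
| 30% | 89% | 95% | 66.5% | +14 | −8.5 |
| 40% | 87% | 95% | 57% | +12 | −18 |
| 100% | 75% | none | 0% | 0 | −75 |

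For e = 20%: 0.80·0.95 + 0.20·0.75 = 0.76 + 0.15 = 0.91. With 113 evaluable SOC patients, 0.20·113 ≈ 23 are forced ties. About 0.75·22.6 ≈ 17 of the diagnoses counted as correct for the algorithm are the ED provider's.

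**Direction.** In the table the fill raises the figure compared with scoring VRT-E as not correct (91% vs 76% at e = 20%). It lowers the figure compared with committed outputs only (91% vs 95%), because P_E is below A_D.

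**A weak algorithm.** With A_D = 60% and ED accuracy 75% throughout, the reported figure is 60% at e = 0, 0.5·60 + 0.5·75 = 67.5% at e = 50%, and 75% at e = 100%. Here abstaining improves the score.

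**The case against.** The fill has a documented rationale. Protocol section 5.1.2 gives ED providers in the VOG arm the task to "take over diagnostic decision-making for patients in whom VOG is equivocal (with consultant input, if available", and notes that the same roles are expected if the device enters practice. Algorithm plus ED fallback therefore approximates intended use. The match is not exact: Table 1 of the protocol makes neurology consultation part of the equivocal pathway but leaves it to routine care in the SOC arm. The gap should not be pressed, because the consultation can be waived and SOC providers may also request one. The rationale stands as a reason to keep the filled figure. It does not make that figure the accuracy of the automated algorithm.

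A reader might go further in several directions that the documents do not support.

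- **That the rule rewards a wider equivocal zone.** With A_D = 95% and ED accuracy 75%, the score falls from 93% to 87% as e rises from 10% to 40%. Abstaining helps only where the algorithm is worse than the ED in the patients it passes over. Since protocol section 9.1 bars SOC-arm results from algorithm changes, this score cannot drive the cut points.
- **That the figure is simply inflated.** The direction depends on the reference, as the working shows. Scoring VRT-E as wrong is one choice of estimand, not the true value. It counts deliberate caution as error.
- **That the borrowed share must be large.** Protocol section 7 gives an example of when the algorithm abstains, not a frequency.
- **That outcomes 3 and 4 use different scales.** Outcome 3 is silent on VRT-E. That leaves its rule unspecified but does not show that it differs.
- **That Phase 3 turns on this figure.** The decision rule in SAP section 2.3 and protocol section 9.3 uses Aim 1 total accuracy and costs, and does not name this outcome.

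**Conclusion.** The rule and the interpretation sentence cannot both stand if any equivocal results occur. As specified, the outcome estimates the accuracy of the algorithm with ED fallback. Its difference from the ED is the committed-output difference multiplied by (1 − e), whichever of the two is better.

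The size cannot be stated from the documents. Under the assumptions above, for e between 10% and 40%, the reported figure lies 2 to 8 points below committed-only accuracy. It lies 7.5 to 30 points above the share that the algorithm itself diagnosed correctly. With no equivocal results there is no distortion. If the ED does worse than 75% in equivocal patients, the filled figure is lower than shown.

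The outcome is exploratory in the SAP and secondary in the protocol. This is a matter of labelling and reporting that should be corrected, but it leaves the primary outcome and the Phase 3 decision rule as they are.

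**What to change.** In SAP exploratory outcome 4, and in protocol secondary outcome 6 to match, specify the following for the SOC arm:

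1. The proportion of patients with a committed algorithm diagnosis.
2. Accuracy among those patients, paired with the ED diagnosis of the same patients.
3. The filled figure as now planned, labelled 'algorithm with ED fallback', with the interpretation sentence corrected accordingly.
4. As a sensitivity analysis, accuracy in all SOC-arm patients with VRT-E scored as not correct.

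State the same VRT-E reporting in exploratory outcome 3, which has no rule at present.

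The cost is SAP wording and a few table rows. No new data are needed. The drawback is that one headline figure becomes several, and none of them alone summarizes the algorithm.
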